$$\text{logit}(\pi)_{ij} = \beta_{0j} + \beta_{1j}\text{treatment}_{ij} + r_j \text{ (Treatment = Student and Supporter text jointly)}$$

Subgroup analyses

We will approach the analysis for students who have ever been eligible for Free School Meals (EverFSM) in two ways. First, we will combine all treatment groups into a single treatment group and then subset to include only those who have ever had free school meals, as recorded on the NPD (EverFSM). Secondly, Model (2) will be extended through the inclusion of a dummy variable for FSM recipients (variable = EverFSM) and a corresponding interaction effect between FSM and treatment to test for a differential impact on FSM recipients. The specifications are:

$$\text{logit}(\pi)_{ij} = \beta_{0j} + \beta_{1j}\text{treatment}_{ij} + r_j \text{ (Domain = EverFSM, Treatment = All groups combined)}$$

$$\text{logit}(\pi)_{ij} = \beta_{0j} + \beta_{1ij}\text{treatment}_{ij} + \beta_{2ij}\text{EverFSM}_{ij} + \beta_{3ij}\text{EverFSM}.\text{treatment}_{ij} + r_j \text{ (Treatment = All groups combined)}$$

As proposed in the protocol, we will also explore whether there is evidence for a differential effect on maths and English outcomes, gender and sitting either English or maths versus sitting both English and maths:

$$\text{logit}(\pi)_{ij} = \beta_{0j} + \beta_{1ij}\text{treatment}_{ij} + \beta_{2ij}\text{Subject}_{ij} + \beta_{3ij}\text{Subject}.\text{treatment}_{ij} + r_j \text{ (Treatment = All groups combined)}$$

$$\text{logit}(\pi)_{ij} = \beta_{0j} + \beta_{1ij}\text{treatment}_{ij} + \beta_{2ij}\text{Gender}_{ij} + \beta_{3ij}\text{Gender}.\text{treatment}_{ij} + r_j \text{ (Treatment = All groups combined)}$$

$$\text{logit}(\pi)_{ij} = \beta_{0j} + \beta_{1ij}\text{treatment}_{ij} + \beta_{2ij}\text{N_Subjects}_{ij} + \beta_{3ij}\text{N_Subjects}.\text{treatment}_{ij} + r_j \text{ (Treatment = All groups combined)}$$

Effect size calculation

The EEF guidance suggests the use of a relative risk ratio (RR) as an effect size for binary outcomes. Consequently, this is what we propose to use here for each of the three models making up our primary outcomes. We note that the primary outcome models proposed here are relatively simple and do not include controls for covariates. This is advantageous given that the RR can vary conditional upon covariate levels and would require the centring of covariates in the logistic model to assess the RR at its average covariate value. However, we do not have this issue with the models proposed here, but the Level 2 random college effect will translate into the odds for students at the average level of success across colleges.

The protocol did not specify the calculation of effect sizes for the primary outcomes but did propose an effect size appropriate to continuous outcomes for class attendance. As noted above, we now propose to treat the model for class attendance using a binomial distribution appropriate to modelling differences in proportions. We therefore propose to use the relative risk ratio as a measure of the effect size for this outcome

We will calculate the relative risk ratio, following a method outlined by Fleiss & Berlin (2009),³⁰ as the measure of effect size, using the results, as appropriate, from the three versions of model (2) above for each of the treatment groups and for the class attendance model.

$$RR = \frac{1 + \exp^{-\alpha}}{1 + \exp^{-\alpha - \beta}} \quad (5)$$

In (5) above α refers to the constant from the logistic model (2) and β refers to the treatment indicator.

³⁰ Cooper, H., Hedges, L. and Valentine, J. *The handbook of research synthesis and meta-analysis*

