Different approaches to the programme are being tested: 1) texts targeted at the student, 2) texts targeted at a study supporter, e.g. a parent or peer identified by the student, or 3) texts targeted at both. The quantitative analysis will estimate the effect size of each intervention compared to the single "business-as-usual" control group. The primary outcome will be the percentage of students that pass their GCSE mathematics or English resit exams after one year (the subject they are receiving texts about). Students' attendance will be considered as a secondary outcome measure.

Study design

POPULATION AND ELIGIBILITY CRITERIA

The intervention is being delivered in further education (FE) colleges in England. FE colleges were selected for the trial because they contain the highest proportion of post-16 students resitting GCSE English and/or maths.

Young people are eligible to take part in the trial if they are:

- Aged 16 or older
- Enrolled at one of the participating colleges in September 2017
- Due to resit GCSE maths and/or English in the 2017/18 academic year.

The developer (BIT) used a targeted recruitment strategy to engage FE colleges with the intervention. An initial screening call was used to gauge colleges' interest and ascertain important information, such as the number of students eligible for the trial. A Memorandum of Understanding (MOU) was sent to interested colleges to sign. The MOU included an overview of the intervention and details

¹ Groot et al. (2017) 'I get by with a little help from my friends Two field experiments on social support and attendance in further education colleges in the UK', http://38r8om2xjhh125mw24492dir.wpengine.netdna-cdn.com/wp-content/uploads/2017/04/Study-Supporter-WP_April-2017.pdf [Accessed 02/11/2017]

² Miller et al. (2016) *Texting Parents: Evaluation report and executive summary*, available at: https://educationendowmentfoundation.org.uk/public/files/Projects/Evaluation_Reports/Texting_Parents.pdf [Accessed 02/11/2017]

³ Kraft, M. A. and Rogers, T. (2015) 'The underutilized potential of teacher-to-parent communications: Evidence from a field experiment', *Economics of Education Review*, 47, pp. 49-63.

⁴ The total number of colleges deviates from the trial protocol (n=32). One college, which had previously been counted as an independent unit, has since been identified as being part of a wider group (i.e. a separate campus rather than separate college).

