⁵ Maths students have one additional exam, and therefore receive an additional reminder text.

about the requirements for participating colleges. College leaders were asked to give their consent and return a signed copy of the MOU to the developer.

Students were recruited to the intervention in September and October 2017 using an online survey provided to college 'project leads' by the Behavioural Insights Team. The survey included information about 'Texting Students and Study Supporters' ('Project SUCCESS') and what would be expected of participants, so that they were able to give informed consent. The survey also included a small number of questions about students' attitudes towards learning and their motivation to study. Students willing to take part were asked to nominate a named study supporter, describe their relationship and provide their study supporters' contact details. Study supporters were not asked to give their consent to take part in the trial, but were able to opt-out of the intervention when the first text message was sent (in early November 2017).

TRIAL DESIGN/ DESCRIPTION OF TRIAL ARMS

Project SUCCESS is being evaluated using a four-armed cluster randomised controlled trial (RCT) with randomisation to each of the four trial arms at the individual level. Clustering within colleges will be accounted for as a fixed effect in the model. The four arms of the trial are:

- Student receives text messages
- Study supporter receives text messages
- Student and study supporter receive text messages
- Control (no text messages)

SAMPLE SIZE

The trial is being conducted in 31 FE colleges.⁶ An average of 123 eligible students per college have given their informed consent to participate in the trial; a total of 3,823 individuals. Students retaking both maths and English have been assigned at random to either the maths or English strand of the intervention, so that approximately 50 per cent are participating in each stand.

NUMBER AND TIMING OF MEASUREMENT POINTS

There will be a single post-intervention measurement point. GCSE resit attainment in maths and English post-treatment will be taken from the National Pupil Database (NPD) in autumn 2018 for all students who participated in the programme in the 2017/18 academic year. Students retaking both English and maths will be randomly assigned to receive texts about just one of these subjects and the primary outcome will be attainment in the subject the student received texts about.

Randomisation

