College 19	30	30	30	30	50	70	120
College 20	14	14	15	15	27	31	58
College 21	46	46	46	47	48	137	185
College 22	43	42	42	43	82	88	170
College 23	45	45	45	44	117	62	179
College 24	25	25	25	25	55	45	100
College 25	64	64	63	64	102	153	255
College 26	18	18	18	17	53	18	71
College 27	12	13	12	13	22	28	50
College 28	21	21	21	21	34	50	84
College 29	73	73	73	73	138	154	292
College 30	71	70	70	71	169	113	282
College 31	17	16	16	17	38	23	61
Total	957	955	954	957	1,912	1,911	3,823

⁷ A further three colleges were initially recruited by BIT, but decided to leave the trial before randomisation.

Calculation of sample size

The primary study outcome has been defined as a binary variable – whether or not the student achieves a pass in their maths or English GCSE resit examination. EEF guidance recommends the use of the relative risk ratio as an effect size measure for binary outcomes.⁸ The Relative Risk Ratio (RR) can be calculated from the log-odds ratio, which itself is parameterized within a logistic regression model; which, in turn, is appropriate for the analysis of binary outcomes, given that it bounds predicted probabilities between zero and unity.

Arguably, the sample size calculation would be based upon the effect size parameterised through the logistic model framework. Unfortunately, as noted by Demidenko⁹ (2007) ‘*there is no consensus on the approach to compute the power and sample size with logistic regression*’. Moreover, McConnell & Vera-Hernandez¹⁰ (2015), following Schochet¹¹ (2013), argue that modelling differences in probabilities is more intuitive. Given the lack of consensus in dealing with power analysis for binary outcomes and, particularly, the lack of an agreed approach for complex logistic models with clustered designs, we have followed standard practice for differences in outcome probabilities, using the binomial variance $[p * (1-p)]$ as the plug-in (e.g. McConell and Vera-Hernandez, 2015). From Maynard and Dong¹² (2013, p. 50), we have the following formula:

$$MDES = M_{J-g^*-1} \sqrt{\frac{\rho\omega(1-R_2^2)}{J} + \frac{(1-\rho)(1-R_1^2)}{P(1-P)Jn}} \quad (1)$$

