²³ We intend to deal with missingness in predictor variables through dummy coding missing as an explicit categorical indicator for each variable included in the model.

²⁴ The BIT texting platform allows the developer to monitor the number of 'bounce-backs' (i.e. messages which could not be delivered). This number is available for each weekly 'batch' of text messages sent.

A common approach to estimating compliance has arisen from Bloom (1984)²⁵ and Imbens and Angrist (1994)²⁶ which use an instrumental variables approach to identify compliance. Allocation to treatment group under randomisation acts as an instrument allowing estimation of treatment on those who have complied with treatment. This approach identifies four possible groups of people in terms of their potential assignment and response to treatment offer:

- Defiers: people who do the opposite to whatever action they are assigned
- Never takers: people who always refuse treatment on offer
- Always takers: people who find treatment whatever their allocation
- Compliers: people who take the treatment if offered, but otherwise do not

We assume that never-takers and always-takers do not contribute to the treatment effect (e.g. Bloom, 2006; p10), leaving a treatment effect created by compliers and defiers. Thus:

$$LATE = \frac{ITT}{E(D|Z = 1) - E(D|Z = 0)} \quad (3)$$

Where LATE is the local average treatment effect and represents the treatment effect as the impact on compliers. Z refers to the instrument, i.e. the group to which a person is allocated through random assignment and D represents treatment received (0 = no, 1 = yes).

In the present design we consider it extremely unlikely that people outside of the treatment group seek out supportive texts in a way that mirrors treatment.²⁷ Consequently, we assume that $E(D|Z = 0) = 0$. Formula 3 then reduces to:

$$TOT = \frac{ITT}{E(D|Z = 1)} \quad (4)$$

Where TOT is treatment on the treated. Typically, the TOT represents a weighted average of always takers and compliers.

We note that we can represent the ITT as an odds ratio or on proportional scale, i.e. the difference between two proportions, and will present both versions in the report, in compliance with EEF guidelines for binomial outcome data. We will calculate ITT and TOT on both scales for all impact analysis undertaken.

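### The reason given for zero text receipt among controls does not cover a control student named as a peer's study supporter, and the numbers apparently held would allow a check

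*SAP*

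**What the plan says.** The Introduction gives examples of who may be a study supporter: "e.g. a parent or peer identified by the student". Under Study design (population and eligibility), students were recruited in September and October 2017 through a survey in which those willing to take part were asked to "nominate a named study supporter, describe their relationship and provide their study supporters' contact details". The trial-arms section describes "randomisation to each of the four trial arms at the individual level", with a control arm that gets no texts. Randomisation followed at the end of October 2017, stratified by college.

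Under Non-compliance with intervention, formula (3) divides the ITT by the difference in receipt between arms. The SAP then argues that "we consider it extremely unlikely that people outside of the treatment group seek out supportive texts in a way that mirrors treatment". "Consequently, we assume that" E(D|Z=0) = 0, it continues, which leaves formula (4). Footnote 27 adds only the possibility of reminders that people send to themselves, which it says the design cannot reveal.

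The Randomisation section discusses spill-over, but only between English and maths for students resitting both. Footnote 21 reports that about 250 students gave their own number in place of a supporter's, and that these cases were spread evenly over colleges and treatment groups.

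**The concern.** Treated and control students attend the same colleges, and a peer may be named as supporter. Nothing in the SAP rules out that the peer is a trial participant allocated to control. If the nominating student is in the supporter-only or joint arm, the texts go to that control student's phone. The stated reason for zero receipt is about controls looking for such texts. It says nothing about controls to whom the programme itself sends them.

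Two things are at stake. The complier estimate may use a denominator that is too large. Some of the ITT contrasts may also compare texted students with a control group that is partly texted. As written, the plan contains no step that would reveal either, although the data needed seem to be available.

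**Working it through.** **Inputs from the SAP.** Table 1 gives arm totals of 957, 955, 954 and 957, out of 3,823 (1,912 English, 1,911 maths). I assume that the columns follow the order in which the arms are listed, so the two supporter-text arms hold 955 + 954 = 1,909 students and the control arm 957. From Calculation of sample size: 31 colleges, 60 students per college per comparison, P = 0.5, intra-cluster correlation 0.1, no treatment heterogeneity, control pass rate 0.30, alpha 0.0167, power 0.8.

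**The plan's own figure.** With 30 degrees of freedom, formula (1) times the binomial standard deviation gives

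MDE = [t(1 − 0.0167/2) + t(0.8)] × √(0.9 / (0.25 × 31 × 60)) × √(0.3 × 0.7) = 6.83 points.

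This reproduces the stated 6.8. It contains no allowance for receipt among controls.

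**How many controls could be texted.** The SAP gives neither the share of peer supporters nor the share of those peers who are in the trial. I assume 10% to 30% for the first, 10% to 50% for the second, and that a quarter of such peers are controls.

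- Low end: 1,909 × 0.10 × 0.10 × 0.25 = 5; 5/957 = 0.5%.
- High end: 1,909 × 0.30 × 0.50 × 0.25 = 72; 72/957 = 7.5%.

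Each nomination is counted as a different control. The texts concern the nominating student's subject. With an even split between subjects and no tendency to name someone in the same subject, about half of these would be about the control's own allocated subject.

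**Effect on an ITT contrast.** Nomination came before randomisation, so nominated students should be spread evenly over the arms. Let c be the share of each arm texted as someone's supporter, a the effect of allocation without such texts, and b_T and b_C what such texts add in the treated and control arms. Then

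difference between arms = a + c × (b_T − b_C).

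- If b_T = b_C, the extra texts cancel and the contrast stays at a.
- If b_T = 0 and b_C = a (full treatment for controls, nothing added for treated students), the contrast is a × (1 − c). This is the upper-end case. A 7.0-point effect becomes 6.97 at c = 0.5%, 6.65 at c = 5% and 6.48 at c = 7.5%.

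In that upper-end case at c = 5%, power for a true 6.83-point effect falls from 0.80 to 0.75, and the effect needed for 80% power rises to 6.83/0.95 = 7.19 points.

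**Effect on the complier estimate.** Write p1 for E(D|Z=1). Formula (4) divides by p1 and formula (3) by p1 − c, so formula (4) gives (p1 − c)/p1 of the formula (3) value. With p1 = 0.90 (assumed):

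- c = 0.5%: 0.895/0.90 = 0.994
- c = 5%: 0.85/0.90 = 0.944
- c = 7.5%: 0.825/0.90 = 0.917

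These ratios count every texted control as D = 1, so they too are upper-end.

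**The case against.** The SAP does not say that peers are fellow resit students, attend the same college or take part in the trial. Rules on who could be nominated may sit in the protocol or the survey, which are not shown. The range for affected controls spans a factor of 15 and rests on assumed shares. This stands, and it is why the size is left open.

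A reader might infer that all three ITT contrasts are pulled towards zero and that both the ITT and the treatment-on-treated estimates are understated. The document does not support that. Because nominees are balanced over the arms, dilution requires supporter texts to add less for treated students than for controls. That is plausible where students already get texts themselves (student-only and joint arms). It is doubtful in the supporter-only arm, whose students get none in their own right and can equally be texted as someone's supporter.

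A reader might also infer that every texted control should count as treated. The SAP's starting definition of compliance is receipt of all texts. A message about another student's study, perhaps in the other subject, need not meet it.

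Finally, the SAP does not state outright that control students' own numbers are held. Footnote 21 and the common survey make it likely, but footnote 21 describes own-number entries, not a match across all participants.

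None of this supplies the missing justification. The reason given for zero receipt still does not address peer nomination.

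**Conclusion.** The point holds in a limited form. Setting E(D|Z=0) to zero rests on a reason that leaves out a route the design allows. The frequency is unknown: 0.5% to 7.5% of controls under the assumed shares. If supporter texts act like treatment for controls and add less for students already texted, the student-only and joint contrasts are diluted, by at most about half a point on a 7-point effect within that range (7.0 − 6.48 = 0.52). Formula (4) then understates the complier effect, by up to about 8% if receipt in the treated arm is 90%. For the supporter-only arm the direction cannot be settled from the document. The primary model and its tests need no change. This is a minor improvement, and confidence that it matters in practice is low until a count exists.

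**What to change.** 1. Match nominated supporters' numbers against all participants' own numbers, keeping own-number entries separate. Report the count of participants nominated by another participant, and of those actually texted, by arm, college and subject.
2. If any controls were texted, estimate E(D|Z=0) with the same compliance threshold as in the treated arms, counting texts about the student's allocated subject, and use formula (3). Repeat with receipt in either subject as a sensitivity analysis. If none were texted, the zero is supported by evidence and formula (4) can stay.
3. Add one ITT sensitivity analysis that excludes, in every arm, participants nominated as a supporter by another participant. Nomination preceded randomisation, so the comparison stays randomised, though for a slightly narrower population.

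The cost is one data match, which depends on students' own numbers being held, and a slightly smaller sample in the sensitivity analysis.

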A multi-site randomisation design was used, with the FE college as the stratifying variable. Students were randomly allocated on a 1:1:1:1 basis to one of four intervention groups (three treatment and one control). It had been agreed at the outset that students retaking both English and maths would receive texts about one subject only. Therefore those students retaking both were randomly allocated to either one or the other outcome group to ensure an overall balanced design, giving an overall average of 31 students per trial arm per college (15/16 per arm, per subject), i.e. an average of 123 students per FE college.

Focusing the design on one subject per person from those taking dual re-sits protects the analysis from potential spill-over effects. For example, a person receiving an English text treatment reminder might also act upon that reminder to do further work on their maths. If that person's maths exam results were included in the non-texting control group this spill-over reminder effect could bias the impact estimate. By allocating dual resit students either to maths or English and removing their results

⁶ Please see footnote 4 for an explanation of how and why this number deviates from the trial protocol.

on the unallocated subject from the analysis, any spill-over effects on the unallocated subject will not be included in the analysis and so cannot influence the results.

Randomisation to each of the four treatment groups was carried out in Stata MP Version 14, using the `.randomise` command with a maximum of 100 randomisations used to achieve balance on the subject taken. The randomisation was conducted at the end of October 2017 by an independent analyst within the evaluation team. Table 1 provides a breakdown of numbers randomised by college and trial arm.

Table 1: Results of the randomisation

College ⁷	Arm 1	Arm 2	Arm 3	Arm 4	Total English	Total maths	Total per college
College 1	51	51	52	51	104	101	205
College 2	8	8	8	9	22	11	33
College 3	18	18	17	18	49	22	71
College 4	8	9	9	9	15	20	35
College 5	42	43	43	43	84	87	171
College 6	22	22	22	22	45	43	88
College 7	26	26	26	25	67	36	103
College 8	33	33	33	32	44	87	131
College 9	23	23	23	24	80	13	93
College 10	29	28	29	28	53	61	114
College 11	33	32	32	32	51	78	129
College 12	6	6	6	6	14	10	24
College 13	50	49	49	49	77	120	197
College 14	27	28	27	27	19	90	109
College 15	22	22	22	22	58	30	88
College 16	51	51	51	52	147	58	205
College 17	13	13	13	13	19	33	52
College 18	16	16	16	15	27	36	63

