- We assume a total of 31 participating colleges and an average of 60 students per college for each of the three pairwise comparisons, with 30 in each treatment arm and 30 in the control (with a broadly even split between maths and English). This means a total of 930 students in each treatment arm and 930 in the control group; a total of 1860 for each of the three pairwise comparisons.
- Maths and English outcomes (i.e. a pass or fail in the English or maths GCSE resit exam) will be considered together as a single outcome variable.
- We assume equal proportions of students in the treatment and control groups ($P = 0.5$) for each pairwise comparison.
- We anticipate a baseline pass rate of 30% ($\theta = 0.3$)
- We have three separate significance tests for the primary outcome, with each of the three treatment groups separately compared to the control group.
- We assume a nominal Type 1 error rate of 0.05 with a two-tailed test, amended using a Bonferroni adjustment for three separate independent tests, to a value of 0.0167 for each test. The Type II error rate is set at 0.2, giving power of 0.8.
- We assume¹⁴ an intra-cluster correlation coefficient (ρ) of 0.1.
- No between site heterogeneity is expected (i.e. $\omega = 0$).
- No level 1 baseline test covariate has been included in the calculation, for reasons explained below. There are also no level 2 stratification variables because we have treated the colleges as random effects and no preliminary stratification was undertaken for college type.
- We assume no attrition in the design, our rationale for which is explained below.
- The EverFSM MDE calculation combined all three treatment arms and assumed a 20% prevalence per college, giving $(90 \times 0.2) + (30 \times 0.2) = 24$ students per college.

The assumptions for each MDE estimation are given in Table 2, below.

The sample size calculations in Table 2 were originally intended to enable the detection of a seven percentage point increase in the GCSE pass rate, from (an estimated) 30 per cent to 37 per cent.¹⁵ However, the underlying model for the purposes of this power calculation, which we have now changed as described above, assumed, a fixed effects model, with no random variation at Level 2, i.e. colleges represented strata from a population fully defined by the sample.

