Analysis of the free school meal (FSM) students will combine all three treatment groups into a single group and compare them to the control group (i.e. a ratio of 3:1). We assume that 20 per cent of the overall group will be EverFSM, i.e. 48 out of 240 in each college.

We understand that the primary concern of the study is whether or not students pass their GCSE resit. Consequently, a binomial pass/fail measure is more appropriate than a continuous outcome for the current study. In addition, it is anticipated that re-sit scores will cluster around the pass/fail threshold, leaving a restricted range of scores on the Level 1-9 scale, which will not be suitable for analysis assuming a continuous measurement scale.²² (Unfortunately, it is not possible to obtain the raw GCSE marks (i.e. a percentages) underlying these grades from the NPD.)

In view of this, we propose that English and maths attainment scores for the end of the academic year of study be taken from the NPD and coded in binary format: a KS4 re-sit pass is defined as attaining level four or above; a fail is defined as reaching levels one to three. We will also classify young people who do not re-sit the exam as a 'fail', in line with the intention-to-treat approach. Outcome data will be obtained by matching pupils at the start of the academic year in the study to their outcome data for the end of the academic year. The outcome estimate will be a pass-rate proportion (a ratio of the number who started the trial and passed the exam divided by number starting the trial) bounded by zero and unity.

Each outcome has four intervention groups: three treatment and one control, and the aim is to test each treatment separately against the control group to determine the efficacy of each treatment. Consequently, we run three paired treatment–control tests. In order to maintain a five per cent significance level for each test, a standard Bonferroni adjustment was applied to account for the three tests in each of the families. This resulted in a value of 0.0167, i.e. $\alpha/3$, and only tests showing a significance level below this threshold will be accepted as statistically significant at $\alpha = 0.05$.

²¹ Analysis suggests that around 250 students entered their own number rather than their study supporter's, but that these cases were evenly distributed across colleges and treatment group. This issue will be discussed in more detail in the final evaluation report.

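### Single-step Bonferroni at 0.0167 is valid, but Holm would give more power at the same family-wise 5%, and the wording on independence and error level needs correcting

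*SAP*

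**What the plan says.** Under Calculation of sample size, the SAP lists three significance tests for the primary outcome, with "each of the three treatment groups separately compared to the control group". It first fixes the overall level: "We assume a nominal Type 1 error rate of 0.05 with a two-tailed test". It then reduces this to 0.0167 per test and describes the step as "amended using a Bonferroni adjustment for three separate independent tests".

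The Primary outcome section gives the purpose: "In order to maintain a five per cent significance level for each test, a standard Bonferroni adjustment was applied". It treats the three comparisons with control as one family. The decision rule follows: "only tests showing a significance level below this threshold will be accepted as statistically significant" at the 0.05 level. This is a single-step rule: every p-value meets the same threshold, whatever the other two tests show.

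Two other statements bear on dependence. The Introduction says that the analysis will "estimate the effect size of each intervention compared to the single" business-as-usual control group. The Randomisation section says: "Students were randomly allocated on a 1:1:1:1 basis to one of four intervention groups". Table 1 shows arms of 957, 955, 954 and 957.

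**The concern.** Three things in these passages do not fit well.

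1. Three contrasts that use the same control students cannot be independent.
2. A threshold of alpha/3 does not hold each test at 5%. It holds each test at 1.67% and the family of three at no more than 5%.
3. Keeping the second and third tests at 0.0167 after one has succeeded is stricter than a family-wise 5% requires. Holm's step-down rule rejects everything that Bonferroni rejects, sometimes more, under the same guarantee.

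The third item has practical weight. The plan's stated aim is to determine the efficacy of each treatment, and one arm combines the other two. Several effective arms is therefore a plausible outcome, and that is where a step-down rule gains most.

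**Working it through.** **Inputs from the SAP.** Two-sided alpha 0.05, three tests, 0.0167 per test, power 0.80, 31 colleges, 60 students per college per comparison (1,860), P = 0.5, intra-cluster correlation 0.1, control pass rate 0.30, no covariates, no between-site heterogeneity, no attrition. Allocation is 1:1:1:1 with one control group.

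**Step 1: reproduce the plan's MDE.** Formula (1) with heterogeneity and both R² at zero, and 30 degrees of freedom:

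- Multiplier: t(1 − 0.0167/2; 30) + t(0.80; 30) = 2.535 + 0.854 = 3.389.
- Standardised standard error: √[(1 − 0.1)/(0.25 × 1,860)] = √(0.9/465) = 0.0440.
- Scale: √(0.3 × 0.7) = 0.4583.
- MDE = 3.389 × 0.0440 × 0.4583 = 0.0683, or 6.83 points. Table 2 gives 6.8.

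The EverFSM column (alpha 0.05, P = 0.75, 24 per college) comes to 10.66 against the stated 10.7. Table 2 is reproduced.

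**Step 2: dependence.** With equal arms, each contrast has variance 2v (v for the treatment mean, v for the control mean). Any two contrasts share the control term, so their covariance is v and their correlation is v/2v = 0.5.

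**Step 3: error rate of the current rule.** At 0.0167 per test (z = 2.394), the family-wise error under the global null is 1 − (1 − 0.05/3)³ = 4.92% if the tests were independent. With correlation 0.5 it is 4.45% (numerical integration). Both are below 5%, so the rule is valid and slightly conservative.

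**Step 4: Holm against Bonferroni.** Holm compares the smallest p-value with 0.05/3 = 0.0167, the next with 0.05/2 = 0.025 and the largest with 0.05, and stops at the first failure. The comparison uses 2,000,000 simulated sets of three z statistics with correlation 0.5. Each effective arm has mean 2.394 + 0.842 = 3.236, which gives 80% power under Bonferroni.

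| Arms that work | Quantity | Bonferroni | Holm |
|---|---|---|---|
| 3 | Power per arm | 0.800 | 0.865 |
| 3 | All three detected | 0.61 | 0.77 |
| 3 | At least one detected | 0.950 | 0.950 |
| 2 | Power per effective arm | 0.800 | 0.828 |
| 2 | False positive in the null arm | 1.7% | 3.9% |
| 1 | Power for the effective arm | 0.800 | 0.801 |
| 1 | False positive per null arm | 1.7% | 2.4% |
| 1 | Family-wise error | 3.2% | 4.2% |
| 0 | Family-wise error | 4.4–4.5% | 4.4–4.5% |

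**Step 5: using the correlation as well.** Step-down Dunnett has thresholds of 0.0188, 0.0270 and 0.05. Its power per effective arm is 0.870, 0.837 and 0.814 with three, two and one effective arms: half a point to 1.3 points above Holm. Its first-step threshold moves the MDE only from 6.83 to 6.73 points.

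**The case against.** The strongest reply is that nothing in the plan is invalid. Bonferroni needs no independence, so the wrong word leaves the 0.0167 threshold, the type I error control and Table 2 as they are. The Primary outcome section does not rely on independence and already refers to families of tests. The plan promises 80% power per comparison, sets no goal of detecting all three effects, and delivers what it promises. All of this stands.

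A reader might infer that the single-step rule loses true positives with no gain in error control. The figures do not support that. Bonferroni gives fewer false positives when some arms work and others do not: 1.7% against 3.9% for the null arm when two work. Holm stays within 5%, but part of its extra power comes from using more of that allowance. In a trial that asks which route works, wrongly endorsing one is a real cost, and preferring the stricter rule is defensible.

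Two further limits stand. The gain from 0.80 to 0.865 is the best case, with all three arms effective; with one effective arm Holm gains almost nothing. And single-step Bonferroni keeps test decisions and simultaneous intervals aligned, which Holm may not.

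What the reply does not remove is that the two statements are wrong as written, and that Holm gives the same family-wise guarantee with never fewer rejections, from p-values the plan already produces.

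**Conclusion.** This is a worthwhile, low-cost improvement to a valid procedure. The tests are correlated at about 0.5, and the 5% is a family-wise level. Holm raises per-arm power by about 6 points if all three arms work and about 3 if two do, with no real gain if only one does; it never changes the chance of at least one success.

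A reader might infer from the word independent that the type I error or the sample size is wrong. Neither is: the actual family-wise error is about 4.45%, and the MDE is reproduced.

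The power figures assume normal test statistics, correlation 0.5, and effects of equal size among the arms that work, set to give 80% power under Bonferroni. The SAP's MDE uses t values with 30 degrees of freedom, so absolute powers would shift slightly, but the ranking of the methods would not.

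**What to change.** - Calculation of sample size: delete the word independent, and note that the three comparisons share one control group. The MDE in Table 2 can stay, since Holm's first step is still 0.0167.
- Primary outcome: replace the claim of 5% for each test with a family-wise 5% across the three comparisons.
- Decision rule: pre-specify Holm for the three primary comparisons, testing the ordered p-values against 0.0167, 0.025 and 0.05 and stopping at the first that fails. If the same adjustment is meant for the three attendance comparisons, say so and use Holm there too.
- Intervals: state the level at which they will be reported, and that Bonferroni-level simultaneous intervals may not match Holm decisions.

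For Holm the cost is SAP wording only; the three separate models are unchanged. The change should be made before outcome data arrive, which the SAP places in autumn 2018, so that it cannot look data-driven. The statistical cost is the fuller use of the 5% allowance shown above.

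Step-down Dunnett is optional. It adds little over Holm and needs the joint correlation of the tests, which the three separate models do not provide. It would need an assumed value of 0.5 or a single four-arm model, and the latter changes the primary analysis.
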